APPENDIX H: SAMPLE SIZE AND EFFICACY ANALYSIS

H.1 Results from Study No. KIT-302-03-01

H.1.1 Study No. KIT-302-03-01 documented that while celecoxib had only minor effects on BP, and amlodipine reduced BP significantly, adding celecoxib to the amlodipine increased the BP reduction. The mean changes in SBP_{day}, DBP_{day}, SBP_{night}, and DBP_{night} from baseline to end of therapy are listed below.

Changes in Blood Pressure from Baseline to End of Therapy (Mean ± Standard Deviation mmHg)

	SBP _{day}	DBP _{day}	SBP _{night}	DBP _{night}
Placebo	-2.1 ± 8.2	-0.3 ± 5.4	-1.4 ± 9.2	0.0 ± 6.2
Celecoxib	-0.5 ± 8.8	-1.5 ± 5.1	-1.7 ± 12.3	0.3 ± 7.1
Amlodipine	-8.8 ± 8.1	-5.5 ± 5.1	-6.4 ± 11.4	-3.2 ± 7.8
Amlodipine + Celecoxib	-10.6 ± 9.2	-7.5 ± 6.4	-10.5 ± 10.6	-7.0 ± 8.6

H.2 Margin

H.2.1 The sample size is to be based on the hypothesis that the mean reduction in SBP_{day} from Day 0 to Day 14 of subjects in the Amlodipine+Celecoxib group (arm 1) minus half the mean reduction in SBP_{day} from Day 0 to Day 14 of subjects in the Amlodipine+Placebo group (arm 2) is at least 0.

H.2.2 The margin is based on a mean reduction of 8.8 mmHg in SBP_{day} for the Amlodipine+Placebo group and a mean reduction of 10.6 mmHg for the Amlodipine+Celecoxib group as seen in the previous study, KIT-302-03-01.

H.2.3 To ensure that at least half the effect is maintained, a value of $10.6 - 0.5(8.8) = 6.2$ mmHg should be set for d (anticipated mean difference) in the sample size formula (see Section 10.9 for formula).

H.3 Standard Deviation

H.3.1 The standard deviation for SBP_{day} with Amlodipine+Placebo was observed to be 8.1 mmHg in the previous study (Study No. KIT-302-03-01).

H.3.2 The standard deviation for SBP_{day} with Amlodipine+Celecoxib was observed to be 9.2 mmHg in the previous study (Study No. KIT-302-03-01).

H.3.3 The pooled standard deviation for the power and sample size justification is 8.7 mm Hg.

H.4 Preliminary Estimate

H.4.1 It is suggested that a preliminary analysis is carried out at $n = 27$ per group. This is based on $\alpha = 0.025$, $\beta = 0.2$ and a conservative estimate of $s = 8.7$. To further optimize the probability of success the actual number is to be increased to 45 per group.

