10.9 Sample Size

- 1) The sample size is to be based on the hypothesis that the mean reduction in SBP_{day} from Day 0 to Day 14 of subjects treated with amlodipine tablets (10 mg) and celecoxib capsules (200 mg) given together (arm 1) minus half the mean reduction in SBP_{day} from Day 0 to Day 14 of subjects treated with amlodipine tablets (10 mg) given alone (with matched celecoxib placebo) (arm 2) is at least 0.
- 2) Formula

Sample size is based on the formula

$$n = \left\lceil 2 \left(\frac{Z_{1-\alpha} + Z_{1-\beta}}{d} \right)^2 s^2 \right\rceil$$

where

s is the standard deviation (8.7)

d is the anticipated mean difference (6.2)

α is the one-sided level of significance (0.05)

$1-\beta$ is the power, one-sided (80%)

$\lceil \rceil$ is the ceiling function

3) Margin

The margin is based on a mean reduction of 8.8 mmHg in SBP_{day} for the Amlodipine+Placebo group and a mean reduction of 10.6 mmHg for the Amlodipine+Celecoxib group as seen in the previous study, KIT-302-03-01. To ensure that at least half the effect is maintained, a value of $10.6 - 0.5(8.8) = 6.2$ mmHg should be set for d .

4) Standard Deviation

The standard deviation is based on an 8.1 mmHg standard deviation for the Amlodipine+Placebo group and a 9.2 mmHg standard deviation for the Amlodipine+Celecoxib group in the previous study (KIT-302-03-01). The pooled standard deviation for the power and sample size justification is 8.7 mmHg.

5) Loss to Follow-up Adjustment

The final sample size is rounded up to allow for a loss to follow-up. The study selected a round number at least 10% larger than the number necessary to protect against potential subjects not fully participating in the entire trial.

Refer to Appendix H for further details regarding the determination of sample size.

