#### **1.3.11. Sample size formula**

Changed the  $\alpha$  (one-sided level of significance) in the sample size formula to 0.025. The protocol listed 0.05 in error. The planned number of subjects (approximately 105) was based on the 0.025 value.

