### 3.1. Sample Size

The sample size was based on findings of the KIT-302-03-01 study, and on the hypothesis that the mean reduction in SBPday from baseline to Day 14 of subjects treated with amlodipine tablets (10 mg) and celecoxib capsules (200 mg) given together (arm 1) minus half the mean reduction in SBPday from Baseline to Day 14 of subjects treated with amlodipine tablets (10 mg) given alone (with matched celecoxib placebo) (arm 2) is at least 0.

Sample size was based on the formula

$$n = \left\lceil 2 \left( \frac{Z_{1-\alpha} + Z_{1-\beta}}{d} \right)^2 s^2 \right\rceil$$

Where:

$s$  is the SD (8.7)

$d$  is the anticipated mean difference (6.2)

$\alpha$  is the one-sided level of significance (0.025)

$1-\beta$  is the power, one-sided (80%)

$\lceil \rceil$  is the ceiling function

The margin was based on a mean reduction of 8.8 mmHg in SBPday for the amlodipine + placebo arm and a mean reduction of 10.6 mmHg for the amlodipine + celecoxib arm as seen in the previous study, KIT-302-03-01. To ensure that at least half the effect is maintained, a value of  $10.6 - 0.5(8.8) = 6.2$  mmHg should be set for  $d$ .

The SD was based on an 8.1 mmHg SD for the amlodipine + placebo arm and a 9.2 mmHg SD for the amlodipine + celecoxib arm in the previous study (KIT-302-03-01). The pooled SD for the power and sample size justification is 8.7 mmHg.

The final sample size was rounded up to allow for a loss to follow-up. The study selected a round number at least 10% larger than the number necessary to protect against potential subjects not fully participating in the entire trial.

Approximately 105 subjects were to be randomized. Therefore, a sufficient number of subjects were to be screened so as to achieve approximately 105 subjects entering the randomization phase (starting at Day 0).

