### **7.7. Primary Efficacy Analysis**

The primary efficacy analysis is to establish the non-inferiority of amlodipine tablets (10 mg) and celecoxib capsules (200 mg) given together (arm 1) with half the effect achieved with amlodipine tablets (10 mg) given alone (celecoxib placebo) (arm 2).

Statistics are based on the change in BP from the baseline ABPM measurement (Day -1 to Day 0) to the post-dose ABPM measurement (Day 13 to Day 14 or if a LOCF is required Day 6 to Day 7), as this represents the efficacy of the treatment. As indicated below, the change will be Day 13 to Day 14 minus Baseline and so a reduction will be a negative number. Sensitivity analysis will compare the results for the ITT population with those of the PP dataset and an MMRM analysis, if possible. A sensitivity analysis will also compare the results with the mITT population.

The hypothesis test being conducted is as follows:

$$H_0: \Delta SBP_{day,1} - 0.5(\Delta SBP_{day,2}) \geq 0 \text{ mmHg}$$

$$H_1: \Delta SBP_{day,1} - 0.5(\Delta SBP_{day,2}) < 0 \text{ mmHg}$$

Where  $\Delta SBP_{day,1}$  is the change, for subjects in arm 1, in the  $SBP_{day}$  from the baseline ABPM measurement ( $SBP_{day,1,base}$ ) to the final ABPM measurement ( $SBP_{day,1,14}$ ).

$$\Delta SBP_{day,1} = SBP_{day,1,14} - SBP_{day,1,base}.$$

$\Delta SBP_{day,2}$  is the change, for subjects in arm 2, in  $SBP_{day}$  from the baseline ABPM measurement ( $SBP_{day,2,0}$ ) to the final ABPM measurement ( $SBP_{day,2,14}$ ).

$$\Delta SBP_{day,2} = SBP_{day,2,14} - SBP_{day,2,base}.$$

This makes the actual test statistic:

$$\delta = \Delta SBP_{day,1} - 0.5(\Delta SBP_{day,2})$$

A one-sided 97.5% CI for  $\delta$  will be computed. In addition, a two-sided non-inferiority t-test comparing  $\delta$  to 0 will provide an appropriate p-value. This p-value will be computing the probability of observing a value  $\geq 0$  from a normal distribution for  $\delta$ .

Refer to the protocol Appendix H for further details regarding the efficacy analysis, and in particular the non-inferiority margin.

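### The 27 per group in Protocol Appendix H.4.1 does not follow from its stated inputs (the printed formula gives 31), and that formula's variance is 1.5 to 1.6 times that of the tested contrast; the final 45 per group is still adequate.

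*Protocol*

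**What the plan says.** Appendix H.4.1 of the protocol, headed Preliminary Estimate, suggests that "a preliminary analysis is carried out at $n = 27$ per group". It gives the basis as alpha = 0.025, beta = 0.2 and s = 8.7, and calls that SD conservative. It then says that "the actual number is to be increased to 45 per group".

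H.2.3 sets d = 10.6 − 0.5(8.8) = 6.2 mmHg and sends the reader to the formula in Protocol 10.9, which is n = 2[(z(1−α) + z(1−β))/d]²s², rounded up. SAP 3.1 repeats it with the same s and d.

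Protocol 10.9 prints a one-sided alpha of 0.05. SAP 1.3.11 calls that an error, changes it to 0.025 and adds: "The planned number of subjects (approximately 105) was based on the 0.025 value".

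The hypothesis in Protocol 10.9 concerns the mean reduction with the two drugs "given together (arm 1) minus half the mean reduction in" daytime systolic pressure in arm 2. SAP 7.7 likewise sets out non-inferiority of arm 1 "with half the effect achieved with amlodipine tablets (10 mg) given alone", with test statistic δ = (change in arm 1) − 0.5 × (change in arm 2). SAP 7.7 also refers the reader to Appendix H for further detail on the efficacy analysis.

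**The concern.** There are two separate mismatches.

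1. The 27 should be reproducible from the inputs printed beside it and the one formula the documents give. It is not.
2. The half-weight on arm 2 is applied to the mean difference d but not to the variance. The formula sizes a plain arm 1 minus arm 2 comparison, which is not the primary test.

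At stake is whether the trial was sized correctly and whether the justification can be traced. Neither document states the power at 45 per group, so a reader cannot judge the margin without repeating the calculation. The sentence in H.4.1 can also be read as announcing an interim look at 27 per group. No interim analysis is described elsewhere, and the heading points to a sample-size estimate.

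**Working it through.** **Inputs**
- d = 6.2 mmHg (H.2.3, Protocol 10.9, SAP 3.1)
- Common SD s = 8.7; arm SDs s1 = 9.2 (amlodipine + celecoxib) and s2 = 8.1 (amlodipine + placebo) (H.3)
- One-sided alpha 0.025 and power 80% (H.4.1, SAP 3.1), so z = 1.9600 and 0.8416, with sum 2.8016
- Final number 45 per group: 105 at 3:3:1 gives 45:45:15

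**Step 1. The stated 27.** The printed formula gives

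2 × (2.8016/6.2)² × 8.7² = 0.20419 × 151.38 = 30.91, so **31**.

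Variants tried:

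| Variant of the printed formula | Raw n | Rounded up |
|---|---|---|
| As stated in H.4.1 | 30.91 | 31 |
| Unrounded pooled SD, 8.65 to 8.667 | 30.56 to 30.68 | 31 |
| t reference, 2n − 2 df | – | 32 |
| One-sided alpha 0.05 (Protocol 10.9 as printed) | 24.35 | 25 (26 by t) |
| s = 8.1 (arm 2 SD only) | 26.79 | 27 |

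Of these, only s = 8.1 gives 27. That is a plausible source, but it is an inference: H.4.1 states 8.7.

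Power at 27 per group by the printed formula is Φ(6.2/√(151.38/27) − 1.960) = 74.5%, below the stated 80%.

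**Step 2. Variance of the tested contrast.** For independent arms of equal size, the variance of mean 1 − 0.5 × mean 2 is (s1² + s2²/4)/n.
- Arm SDs: 9.2² + 8.1²/4 = 84.64 + 16.40 = 101.04
- Common SD: 1.25 × 8.7² = 94.61
- Printed formula: 2 × 8.7² = 151.38

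Ratios: 151.38/101.04 = 1.50 and 151.38/94.61 = 1.60.

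Required n per group for 80% power:
- Arm SDs: 101.04 × (2.8016/6.2)² = 20.63, so **21** (22 by t)
- Common SD: 94.61 × (2.8016/6.2)² = 19.32, so **20** (21 by t)

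**Step 3. Adequacy of 45 per group,** with all 45 analysed.
- Printed variance: Φ(6.2/√(151.38/45) − 1.960) = 92.2% (91.7% by t)
- Contrast, arm SDs: Φ(6.2/√(101.04/45) − 1.960) = 98.5% (98.3% by t)
- Contrast, common SD: 99.0%

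Adding the 10% allowance in Protocol 10.9 to the larger requirement gives 31 × 1.1 = 34.1, so 35, still below 45.

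**The case against.** The strongest reply is that nothing in the trial turns on this. H.4.1 replaces 27 with 45 in its next sentence, the 27 does not appear in the SAP, and 45 exceeds every recomputed requirement. The current SAP is a post-unblinding version, so planning figures no longer drive a decision. All of that stands, and it is why the point is minor.

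A second reply is that a planning variance that is too large is a legitimate cautious choice. That is fair, and keeping the formula with a label is one of the two remedies offered. But neither document says the choice was deliberate: the remark about conservatism in H.4.1 describes the SD, not the form of the variance.

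Third, 27 per group would not have been too few for the primary test: against the contrast variance it gives 89.3% power (arm SDs) or 91.2% (common SD). That is correct. The figure is irreproducible rather than dangerous.

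Fourth, 27 can be reached by other routes: s = 8.1 at alpha 0.025, or alpha 0.05 with the 10% allowance (24.35 × 1.1 = 26.8). Each contradicts an input stated in H.4.1, and SAP 1.3.11 disowns the 0.05. They suggest a slip in one input but do not make the statement right.

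Finally, the power figures assume complete data. With about 10% loss, so 40 per group, they fall to 89.0% (printed variance) and 97.4% (contrast, arm SDs). The restated power should say that it is for 45 analysed per group.

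**Conclusion.** The concern holds, as a minor point. The stated 27 per group should be 31 on its own inputs, a gap of 4. The printed formula is not the one for the primary test: it overstates the variance of the contrast by a factor of 1.50 with the arm SDs, or 1.60 with a common SD. The two mismatches pull in opposite directions, and the final 45 per group is adequate under every version examined.

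This rests on the previous study's means and SDs holding in this population, on independent arms, and on equal numbers in arms 1 and 2. The achieved 6:6:1 randomization reported in SAP 3.2 keeps those two arms equal, so it does not disturb the conclusion. Using a t instead of a normal reference moves the required n by one and does not alter it either.

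**What to change.** Choose one of two corrections and apply it consistently in Protocol Appendix H.4, Protocol 10.9 and SAP 3.1, with one-sided alpha = 0.025 throughout.

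- **Option A: use the variance of the tested contrast.** Replace the formula with n = (z(1−α) + z(1−β))² × (s1² + s2²/4)/d², with s1 = 9.2, s2 = 8.1 and d = 6.2. State that about 21 per group are needed for 80% power and that 45 analysed per group gives about 98.5%.
- **Option B: keep the printed formula.** State that 2s² is conservative for arm 1 minus half of arm 2, replace 27 with 31, and state about 92% power with 45 analysed per group.

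Option A matches the primary test directly; Option B changes less text. With either, the sponsor should confirm that H.4.1 refers to a preliminary sample-size estimate and reword the sentence so that it cannot be taken for an interim analysis.

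The cost is a few restated planning figures and one reworded sentence. Enrolment and analysis are unaffected.

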APPENDIX I: CHILD-PUGH CLASSIFICATION OF LIVER CIRRHOSIS

The Child-Pugh score is based on five clinical measures of liver disease. Each measure is scored 1-3 as outlined in the table below.

Measure	1 Point	2 Points	3 Points
Bilirubin ($\mu\text{mol/L}$)	<34	34-50	>50
Serum albumin (g/L)	>35	28-35	<28
Prothrombin time (s prolonged)	<4	4-6	>6
Ascites	None	Mild	Marked
Encephalopathy	None	Mild	Marked

Chronic liver disease is classified into Child-Pugh Classes A to C based on the added score from above. Subjects with Child-Pugh Class B or C cirrhosis will be excluded from this trial.

Points	Class
5-6	A
7-9	B
10-15	C

References

## ABBREVIATIONS

ABPM	ambulatory blood pressure monitor
ADR	Adverse Drug Reaction
AE	Adverse Event
ANCOVA	Analysis of Covariance
ANOVA	Analysis of Variance
ATC	Anatomical Therapeutic Chemical
BE	bioequivalence
BLQ	below limit of quantification
BMI	Body Mass Index
BP	blood pressure
BUN	Blood urea nitrogen
Ca	calcium
CI	Confidence Interval
CRF	Case Report Form
CRO	Contract Research Organization
CS	Clinically Significant
DBP	diastolic blood pressure
DBP 24h	average 24-hour ambulatory diastolic blood pressure
DBP day	average daytime (9:00 to 21:00) ambulatory diastolic blood pressure
DBP night	average night-time (01:00 to 06:00) ambulatory diastolic blood pressure
DDI	drug-drug interaction
ECG	electrocardiogram
FCDP	fixed combination drug product
IB	Investigator's Brochure
ITT	Intent-To-Treat
LLOQ	Lower Limit of Quantification
LOCF	last observation carried forward
MedDRA	Medical Dictionary for regulatory activities
mITT	modified intent-to-treat
NCS	Not clinically significant
NSAID	non-steroidal anti-inflammatory drug
OE	over-encapsulated
PI	Principal Investigator
PK	Pharmacokinetic
PP	Per-Protocol
PT	Preferred Term
PTAE	pre-treatment adverse event
qd	once a day
SAE	Serious Adverse Event
SAP	Statistical Analysis Plan
SAS	Statistical Analysis System
SBP	systolic blood pressure
SBP 24h	average 24-hour ambulatory systolic blood pressure
SBP day	average daytime (9:00 to 21:00) ambulatory systolic blood pressure
SBP night	average night-time (01:00 to 06:00) ambulatory systolic blood pressure
SD	Standard Deviation
SOC	System Organ Class
TEAE	Treatment Emergent Adverse Event
UAE	Unexpected adverse event
UV	ultraviolet
WHO-DD	World Health Organization-Drug Dictionary

## 1. Introduction

This Statistical Analysis Plan (SAP) describes statistical analyses for KIT-302-03-02 study.

### 1.1. Background

KIT-302 is an oral fixed combination drug product (FCDP) consisting of the non-steroidal anti-inflammatory drug (NSAID) celecoxib and the calcium (Ca) channel blocker antihypertensive drug amlodipine besylate. KIT-302 is being developed as a “convenience reformulation” FCDP intended to facilitate and improve patient compliance with the once a day (qd) administration of its individual components, amlodipine and celecoxib, when used together for the intended patient population. It is also intended to provide prescribers with detailed data on how the combination affects the antihypertensive effect of the calcium channel blocker.

The proposed indications in the usage section of the KIT-302 product labeling are anticipated to read as follows: “KIT-302 is indicated for patients who require the use of a NSAID for chronic treatment for the relief of the signs and symptoms of osteoarthritis and who also require the treatment of hypertension to lower blood pressure. Lowering blood pressure reduces the risk of fatal and nonfatal cardiovascular events, primarily strokes and myocardial infarctions.” KIT-302 is not indicated to treat any other type of pain, and is not indicated for short term or intermittent treatment of osteoarthritis.

The formulation of KIT-302 consists of celecoxib and amlodipine besylate co-formulated in a single immediate release tablet. The dosage form was developed so that it would show bioequivalence (BE) to the individually marketed prescription celecoxib capsules and amlodipine besylate tablets given together.

In 2015, Kitov completed a phase 3 pivotal study (KIT-302-03-01) comparing amlodipine besylate monotherapy at a dose of 10 mg/day [over-encapsulated (OE) 10 mg amlodipine tablet + matched placebo for OE celecoxib capsule], with the combination of the components of KIT-302 at a dose of 10 mg amlodipine plus 200 mg celecoxib/day (OE 10 mg amlodipine tablet + OE 200 mg celecoxib capsule). The study also included a double placebo arm and a celecoxib monotherapy arm at a dose of 200 mg/day (matched placebo for OE amlodipine tablet + OE 200 mg celecoxib capsule). Adult subjects with newly diagnosed hypertension who required pharmacological therapy to control their hypertension were randomized to one of the four treatment arms and treated for two weeks. Subjects underwent 24-hour ambulatory blood pressure monitoring at baseline, during the initial 24 hours of therapy, after one week of therapy and after two weeks of therapy.

Study No. KIT-302-03-01 documented that while celecoxib had a negligible effect on blood pressure (BP), and amlodipine reduced BP significantly, adding celecoxib to the amlodipine did not impair the antihypertensive effects of amlodipine but rather tended to enhance amlodipine’s effect, although the synergistic effect only reached statistical significance for average night-time (01:00 to 06:00) ambulatory diastolic blood pressure (DBPnight) and average 24-hour ambulatory diastolic blood pressure (DBP24h). The trending towards a synergistic antihypertensive effect was an unexpected finding, however this finding was consistent throughout the study’s data whether measuring daytime or night-time systolic blood pressure (SBP) or diastolic blood pressure (DBP), and whether measuring BP by using the ambulatory blood pressure monitor (ABPM) device or by taking the measurement manually in the clinic. This internal consistency strongly suggested that the effect is real. Study No. KIT-302-03-02 was designed to confirm this effect.

In attempting to explain the synergistic antihypertensive effect, a review of the plasma concentrations of amlodipine in the two amlodipine-receiving treatment arms was performed. This analysis documented a lower plasma concentration of amlodipine in the treatment arm receiving both celecoxib and amlodipine compared to the treatment arm receiving only amlodipine. It can therefore be concluded

that the enhanced antihypertensive effect when celecoxib was added was not due to an increased amlodipine plasma concentration through some pharmacokinetic (PK) drug-drug interaction (DDI).

An alternative explanation for the antihypertensive synergistic effect may be found in the renal data. Specifically, although patients treated with amlodipine had improved renal function as evidenced by a decreased serum creatinine, there was a trend towards an even greater reduction in serum creatinine among patients treated with both amlodipine and celecoxib. Such an enhancement in renal function might be expected to improve BP control and thus, at least partially explains the synergistic antihypertensive effect. However, since this renal synergy did not reach statistical significance, confirmation would require future clinical investigations. Study No. KIT-302-03-02 was designed to confirm this effect.

Further evidence for a renal component in the synergistic antihypertensive effect can be identified in the adverse event (AE) tables. Specifically, patients treated with amlodipine had a nearly 16% reporting rate of peripheral oedema; such an adverse reaction has been a long-recognized side effect of amlodipine. However, among those patients receiving both amlodipine and celecoxib, the rate of reported peripheral oedema was nearly halved. Thus, it would appear possible that the addition of celecoxib to amlodipine is in some way acting as a diuretic, thereby preventing the peripheral oedema and thus, enhancing the antihypertensive effect. Since this indirect measure of renal synergy did not reach statistical significance, confirmation would require future clinical investigations. Study No. KIT-302-03-02 was designed to confirm this effect.

## 1.2. Statistical Analysis Plan Summary

This Statistical Analysis Plan (SAP) describes the statistical analysis for the KIT-302-03-02 study. The SAP provides full details of the analyses, the data displays and the algorithms to be used for data derivations. The analysis will be done using statistical software Statistical Analysis System (SAS) version 9.4 or higher.

